### Sponsor's reporting of Serious Adverse Events and Device Deficiencies

The Sponsor is responsible to report to the CA's where the clinical investigation has commenced:

- Any SAE that has a **causal** relationship with the investigational device, the comparator or the investigation procedure or where such causal relationship is reasonably possible;
- Any Device Deficiency that might have led to a SAE if:
  - a) Appropriate action had not been taken or,
  - b) Intervention had not occurred or,
  - c) If circumstances had been less fortunate
- New findings/update in relation to already reportable events.

These 'reportable events' must be reported within the following timelines:

- A reportable event which results in imminent risk of death, serious injury, or serious illness that requires prompt remedial action for other patients/subjects, users or other persons or a new finding to it must be reported immediately, but not later than **2 calendar days** after awareness by

the sponsor of a new reportable event or of new information in relation with an already reported event.

- Any other reportable event or a new finding/update to it must be reported immediately, but not later than **7 calendar days** following the date of awareness by the sponsor of the new reportable event or of new information in relation with an already reported event.

### Overview reporting requirements

	WHAT	HOW	TO	TIMELINES
Investigator	AE	AE form	sponsor	as defined in protocol
	SAE	SAE form	sponsor	asap, but no later than 3 calendar days after awareness
	Device Deficiency (DD)	DD form + AE/SAE form (if applicable)	sponsor	as defined in protocol (exception: within 3 calendar days if considered reportable event)
	death	SAE form	sponsor	asap
Sponsor	all reportable events (of all participating sites)	EU SAE report form (excel) 	
 
CA for Belgium -> FAGG: via mail to [contact]
 
PI's of participating sites
 
	asap, but no later than 
 
2 calendar days (in case of risk of death or serious injury/illness that requires prompt remedial action for other patients, users or other persons)
 
7 calendar days (all other reportable events)
 

	death	SAE form + narrative	
 
CA for Belgium -> FAGG: via phone and mail
 
	asap

 The SAE report form in excel format can be downloaded from the following web page: [https://ec.europa.eu/health/sites/health/files/md\\_sector/docs/md\\_mdcg\\_2020-10-2\\_guidance\\_safety\\_report\\_form\\_en.xlsx?web=1](https://ec.europa.eu/health/sites/health/files/md_sector/docs/md_mdcg_2020-10-2_guidance_safety_report_form_en.xlsx?web=1)

### 3.5.15. Vulnerable population

No vulnerable population will be involved in this study.

### 3.5.16. End, suspension or premature termination of the clinical investigation

The clinical investigation will not be suspended or terminated prematurely in any of the investigation sites unless the local PI of the study in an investigation site is unable to recruit or follow up the clients that participate in this study because of for example sickness.

The competent authority (CA) shall be notified by the PI of the KU Leuven at the end of the clinical investigation, and a justification shall be provided in case of a temporary study halt or early termination. The PI will provide the CA with a clinical investigation report.

This must be done in accordance with the MDR:

In accordance with MDR article 77 study end reporting is mandatory within 15 days (but 24 hours if based on safety grounds). In addition, a clinical investigation report needs to be submitted within one year of the end of the clinical investigation or within three months of the early termination or temporary halt. The end of a clinical investigation shall be deemed to coincide with the last visit of the last subject unless another point in time for such end was set out in the clinical investigation plan.

Participants of the clinical investigation are clients in the hearing centre/university hospital. Termination of the clinical investigation will not affect the relationship with their hearing care provider or their regular health care.

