##### *Data Management*

The Trial Data Manager (here coordinating investigator) will perform extensive consistency checks on the received data. Queries will be issued in case of inconsistencies in accordance with internal procedures. A Data Management Plan (DMP) will be developed to map data flows, data validation measures that will be taken, how (interim) database lock(s) will be managed and, as applicable, the role and responsibilities of the Data Safety Monitoring Committee (DSMB)

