### 3.5.10. Deviations from the CIP

#### 3.5.10.1. Protocol / GCP compliance

The Trial must be performed in accordance with the protocol, current ICH and ICH-GCP guidelines, and applicable regulatory and country-specific requirements. ICH guidelines are an international ethical and scientific quality standard for designing, conducting, recording, and reporting studies that involve the participation of human participants. Compliance with this standard provides public assurance that the rights, safety, and well-being of Trial participants are protected, consistent with the principles that originated in the most recent version of the Declaration of Helsinki, and that the Trial data are credible, reliable and reproducible.

The Investigator and Trial team acknowledge and agree that prospective, planned deviations or waivers to the protocol are not permitted under applicable regulations on clinical studies. However, should there be an accidental protocol deviation, such deviation shall be adequately documented in the source documents and on the relevant forms and reported to the CI and Sponsor. Deviations should also be reported to the EC as part of the EC's continued review of the Trial (e.g. through the ASR, APR, etc.). Protocol deviations which are found to frequently recur, will require (immediate) action. The Investigator acknowledges that such recurring protocol deviations could potentially be classified as a serious violation of ICH and/or the protocol.

It is understood that "a serious violation" is likely to affect to a significant degree:

- the safety or physical or mental integrity of the Trial participants; or
- the scientific validity of the Trial

The Investigator is expected to take any immediate action required to protect the safety of any participant included in the Trial, even if this action represents a deviation from the protocol. In such cases, the Sponsor should be notified of this action and the EC at the Trial site should be informed according to local procedures and regulations.

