#### 3.5.14.5. Reporting requirements to Ethics Committees (ECs) and Competent Authorities (CAs)

The Investigator is responsible for ensuring that all safety events are recorded in the (e)CRF and reported to the Sponsor in accordance with instructions provided below.

The Sponsor will promptly evaluate all SAEs, AESIs and Device Deficiencies against medical experience to identify and expeditiously communicate possible new safety findings to Investigators, ECs and applicable CA's based on applicable legislation.

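### Section 3.5.16 limits suspension or early termination to one operational ground, yet the same section sets a reporting deadline for an end on safety grounds; the two must be reconciled

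*Combined protocol and SAP*

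**What the plan says.** Section 3.5.16 begins: "The clinical investigation will not be suspended or terminated prematurely in any of the investigation sites unless the local PI of the study" at a site "is unable to recruit or follow up the clients that participate in this study because of for example sickness". The next paragraph has the KU Leuven PI notify the competent authority at the end of the investigation and adds that "a justification shall be provided in case of a temporary study halt or early termination". The section then cites the MDR: "study end reporting is mandatory within 15 days (but 24 hours if based on safety grounds".

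Other sections bear on the point:

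- Section 3.5.14.5: "The Sponsor will promptly evaluate all SAEs, AESIs and Device Deficiencies against medical experience to identify and expeditiously communicate possible new safety findings" to investigators, ethics committees and authorities. Its subsection on sponsor reporting gives the shortest reporting time to events carrying imminent risk of death, serious injury or "serious illness that requires prompt remedial action for other patients/subjects, users or other persons".
- Section 3.5.10.1: "The Investigator is expected to take any immediate action required to protect the safety of any participant included in the Trial", even where this departs from the protocol.
- Section 3.5.9 lets amendments made for urgent reasons take effect before committee or authority review.
- Section 3.5.14.1, on mitigating privacy-related events, says that university safety measures are activated after a reported data leak.
- Section 3.5.8.1, under Data Management, says a data management plan will cover, "as applicable, the role and responsibilities of the Data Safety Monitoring Committee (DSMB".

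**The concern.** The section headed for suspension and termination is where a site or the sponsor would look to learn whether the study can be paused. Its opening sentence admits one exception, and that exception is operational. A few lines later the section assumes that a safety-based end is possible. A reader cannot follow both.

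Local PIs are trained on this document at site initiation, so a literal reading could cause doubt or delay when a safety finding arises. The device is not CE-marked, and the plan lists over-loud or uncomfortable stimuli and data or server security among its adverse events of special interest. The sponsor evaluates such events, but the plan does not say how that evaluation connects to the rule in 3.5.16.

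**Working it through.** This is a question of wording and the plan states no figure to reproduce, so the check sets the passages side by side.

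**Step 1. Is the opening rule closed?** It has the form of a prohibition with a single exception. The words introducing sickness as an example explain why a local PI might be unable to act. They illustrate the one exception and add no further ground for stopping. Safety is not among the permitted grounds.

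**Step 2. Does the same section assume otherwise?** Yes, twice. It asks for a justification of a temporary halt or early termination, and it gives a 24-hour reporting time for an end on safety grounds. Both lines say what to report and when. Neither creates a ground for stopping. The conflict is therefore between a closed list of grounds and a reporting duty that presupposes a ground outside the list.

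**Step 3. Does the difference between site and study remove the conflict?** The opening sentence speaks of sites and the reporting line of the study. Ending the study means ending it at every site, so a bar on ending it at any site bars ending it as a whole. The conflict remains.

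**Step 4. Does another section supply the missing ground?**

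| Section | What it provides | What it leaves open |
|---|---|---|
| 3.5.9 | Urgent amendments before approval | Names no ground for stopping |
| 3.5.10.1 | Immediate protective action, even as a deviation | Addressed to the investigator; gives the sponsor no rule for a site or the study |
| 3.5.14.5 and its sponsor-reporting text | Evaluation, communication, reporting to authorities | No suspension or termination step |
| 3.5.14.1, privacy mitigation | University measures after a data leak | The procedure is not in the documents, so whether it covers suspending access cannot be judged |
| 3.5.8.1, Data Management | A safety board, where applicable | Role deferred to another document; no stopping role given |
| 3.5.6.2, 3.5.6.3, 3.5.6.4, withdrawal text | Voluntary withdrawal of individuals | Does not concern a site or the study |

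None states a ground on which the sponsor may suspend a site or the investigation.

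**Step 5. Who is affected?** Section 3.5.7.1 plans 75, 60 and 60 hearing-aid users per group in Arms 1, 2 and 3, and 15 CI users per group in Arm 1. Planned app users: 75 + 60 + 60 + 15 = 210. As a check, the total is 390 + 30 = 420, and 420 / 2 = 210.

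**Step 6. Over what recruitment period?** Arms 1 and 3 each recruit for at most 12 weeks. For Arm 2 the plan disagrees with itself: the introduction to 3.5.6.3 gives 9 consecutive months, while its recruitment text gives April 2023 to August 2024. Counting both end months, that is 9 (April to December 2023) + 8 (January to August 2024) = 17 months. Only the 60 app users of Arm 2 belong to that period.

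**The case against.** The strongest reply is that the opening sentence is a clumsy statement about continuity at sites, and that the section read as a whole takes a safety stop for granted. That is probably how it arose, and nothing suggests a deliberate decision to rule out safety. It does not cure the text, because the sentence is still the only rule on grounds in the section devoted to them. Likewise, 3.5.12 commits the trial to the MDR and other law, which would in practice bind the sponsor to act. That makes the mismatch plainer without removing it.

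The partial cover is real. Section 3.5.10.1 is not confined to one individual and expressly permits departing from the protocol. Section 3.5.9 means the sponsor is not locked into the sentence. The data-leak measures partly answer the server-security case.

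The harm argument also stands. Section 3.5.4.2 calls software failures frequent but of minimal severity, with negligible potential harms and the app used on top of standard care. Section 3.5.14.1 describes volume controls against over-loud output.

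Two stronger readings should therefore be resisted:

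- A reader might infer that the sponsor would be powerless to halt enrolment or app access. The sections just named do not support that.
- A reader might infer that participants would keep starting the app for 17 months after a safety signal. That requires a signal on the first day, no use of any of those provisions, and the longer of two conflicting recruitment periods.

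**Conclusion.** The contradiction stands. Section 3.5.16 states a closed rule that omits safety, and the same section provides for reporting an end on safety grounds. No other section gives the sponsor a ground for suspending a site or the investigation, so this is a stated rule in conflict with the plan's own text and goes beyond missing detail.

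Its reach is the 210 planned app users. Its expected consequence is small on the plan's own risk assessment, and the finding does not depend on injury being likely. The length of Arm 2 recruitment cannot be used to size it until the 9-month and April 2023 to August 2024 statements agree. The conclusion rests on a literal reading of the opening sentence and on the documents supplied; the data management plan and the university's breach procedure were not available.

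**What to change.** By amendment, reconcile the exclusive opening sentence of 3.5.16 with the halt and 24-hour safety lines in the same section, and with 3.5.9, 3.5.10.1, the data-leak text in 3.5.14.1 and the sponsor's evaluation and reporting duties in 3.5.14.5. After the change, the plan should no longer contradict itself on whether a safety-based suspension or termination can occur. The grounds, thresholds and decision-maker are for the sponsor to set; none is proposed here. The two statements of the Arm 2 recruitment period in 3.5.6.3 could be aligned in the same amendment.

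The cost of the 3.5.16 change is one or two sentences of amendment text, with no added procedures or staff.

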### 3.5.17. Publication policy

If the results of the clinical investigation will be submitted for publication, we will opt for a mix of gold and green open access for the produced results. Articles that are published in journals that do not grant open-access online will be self-archived after publication in the online repositories.

### 3.5.18. COVID related precautions

Our studies can be conducted safely when the right precautions are taken regarding COVID. Hearing centres and hospitals have very strict COVID regulations. In case any tests need to be performed in our lab, we have specific rules and a protocol to test participants during the COVID pandemic.

